5.2 Exclusion Criteria

- COVID-19 diagnosed based on clinical criteria

6 STUDY PROCEDURES

6.1 Subject Identification

Most PLWHIV will be identified from sites in the NEAT ID network. PLWHIV are routinely followed-up at specialised outpatient clinics with regular follow up visits as standard of care.

Since March 2020, more than 50 European sites have registered and started to provide basic information about the number of PLWHIV with COVID-19 and disease outcomes at their centres (<https://www.NEAT-ID.org/>). The dashboard provides a first estimate about the total numbers of PLWHIV with COVID-19 and where these patients are in continued care. As of 26th April 2021, 1,187 PLWHIV with COVID-19 were reported in care across Europe, with 436 hospitalisations and 78 deaths from an estimated number of 85,279 PLWHIV in routine care at these sites. These case numbers strongly suggest feasibility to recruit sufficient numbers of PLWHIV with COVID-19 and that patients have been identified at their centres already.

6.2 Data collection

Only real-world retrospective data will be used for this study. Deidentified retrospective data will be transcribed into the eCRF system from source data at each clinical site or from existing COVID-19 cohort databases, where appropriate. No personal identifiable data will be transmitted to NEAT ID. The data elements will be transcribed from source data according to the data collection list below. Mechanisms to ensure data quality and integrity will be deployed as per applicable standard operating procedures and in line with GCP and GPP. Patients and controls will be identified and documented by participating sites, provided unbiased matching for inpatient/outpatient status at the time of COVID-19 diagnosis is ensured. Alternatively, and to avoid potential site-related bias during selection of HIV negative controls with COVID-19 diagnosed in hospital, data from matched controls will be obtained from appropriate existing COVID-19 cohort databases, e.g. LEOSS (Lean European Open Survey on SARS-CoV-2 infected patients) or ISARIC (International Severe Acute Respiratory and emerging Infection Consortium).

For all patients the following information will be collected:

- Age
- Sex
- Ethnicity (where available)
- Comorbidities (see appendix 1)
- Weight (kg) and height (m) (to calculate BMI)

For patients with COVID-19 the following information will be collected (where applicable):

- Date of positive PCR test result (documented or patient-reported)
- COVID-19 diagnosis inpatient or outpatient
- All-cause mortality in hospital, or palliative discharge, or mortality at 6 weeks after diagnosis of COVID-19 or at discharge from hospital
- Hospitalisation for COVID-19 and length of hospitalisation
- Critical care admission (high dependency unit or intensive care unit) for COVID-19 and length of stay in critical care
- Length of invasive ventilation
- Length of extracorporeal membrane oxygenation (ECMO)
- Need for kidney replacement therapy
- Inflammatory markers and blood cell counts at COVID-19 diagnosis¹ (if available):
 - Full blood cell count (Platelet count, RBC Count, WBC count (absolute), Haemoglobin, Haematocrit, MCV, MCH, Neutrophils, Lymphocytes, Monocytes, Eosinophils, and Basophils), ALT, AST, total bilirubin, urea, serum creatinine, calcium, glucose and HbA1C levels, total cholesterol, triglycerides, CRP, D-dimer, ferritin, and lactate dehydrogenase
- Drug treatment for COVID-19 (glucocorticoids, azithromycin, remdesivir, monoclonal antibodies against SARS-CoV2, convalescent plasma, anti-IL1 inhibitors, anti-IL6 inhibitors, lopinavir/ritonavir, and others)

For PLWHIV the following information will be collected:

- Date of HIV diagnosis
- Current ART
- CDC disease stage
- CD4 cell nadir
- Last CD4 cell count (including CD4% and CD4/CD8 ratio) and HIV-RNA before COVID-19 diagnosis, or most recent for HIV-only controls

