4.1 Study Schema

[figure not shown]

Figure 1: Study design with cases (PLWHIV & COVID-19) and two matched control groups.

In total, 500 cases and up to 2500 controls will be analysed.

Only real-world retrospective data will be used for this study. Deidentified retrospective data will be transcribed into the eCRF system from source data at each clinical site or from existing COVID-19 cohort databases, where appropriate.

For comparing PLWHIV & COVID-19 versus HIV seronegative COVID-19 patients, a 1:1 and 1:3 matching will be performed according to the following criteria:

- Age (+/- 5 years)
- Sex
- Ethnicity (where available)
- Month of COVID-19 diagnosis (+/- 2 months)
- COVID-19 diagnosis inpatient, 1:1 matching
OR
- COVID-19 diagnosis outpatient (ambulatory), 1:3 matching

For comparing PLWHIV & COVID-19 versus PLWHIV without COVID-19, a 1:2 matching for similar risk of acquiring COVID-19 will be performed according to the following criteria:

- Age (+/- 5 years)
- Sex
- Ethnicity (where available)

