5.1 Inclusion Criteria

- Cases (PLWHIV + COVID-19)
 - Any gender
 - At least 18 years of age
 - Documented HIV-1 infection
 - Confirmed SARS-CoV-2 infection by documented, or patient-reported, positive result on PCR testing of a nasopharyngeal or respiratory sample, before 1st April 2021

Each case should be matched to a control (1:1 or 1:3 respectively for COVID-19 controls and 1:2 for PLWHIV controls) according to the matching criteria set out in section 4.1.

- Controls (COVID-19)
 - Any gender
 - At least 18 years of age
 - No documented HIV-1 infection
 - Confirmed SARS-CoV-2 infection by documented, or patient-reported, positive result on PCR testing of a nasopharyngeal or respiratory sample, before 1st April 2021
 - Meet the matching criteria
- Controls (PLWHIV)
 - Any gender
 - At least 18 years of age

- Documented HIV-1 infection
- No evidence of SARS-CoV-2 infection
- Meet the matching criteria

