7.3.2 Primary outcome analysis

The first primary outcome analysis will be performed on PLWHIV with COVID-19 versus HIV uninfected individuals with COVID-19. The endpoint is the occurrence of critical care admission (high dependency unit or intensive care unit), mortality in hospital or palliative discharge when discharged from hospital, or mortality at 6 weeks after diagnosis of COVID-19 or at discharge from hospital (where applicable). Kaplan-Meier estimates will be used to estimate the proportion of participants with the primary endpoint events. Unadjusted and adjusted hazard ratios (HR) will be estimated using the Cox proportional hazard model to assess the impact of HIV-infection on the severity of COVID-19. The validity of the proportionality assumption will be assessed and tested. The adjusted variables will be the following (potential confounders): Age (<60 vs 60-64 vs 65-69 vs 70-74 vs ≥75 years); Sex at birth (female vs male); Obesity (BMI>30 kg/m²); and Comorbidities (see appendix 1).

The second primary outcome analysis will be performed within the group of PLWHIV (PLWHIV with COVID-19 versus PLWHIV without COVID-19). The endpoint is to assess factors associated with severe COVID-19 within the group of PLWHIV. Conditional logistic regression models will be used to account for the case-control matching. The following variables will be assessed: Age (<60 vs 60-64 vs 65-69 vs 70-74 vs ≥75 years); Sex at birth (female vs male); Obesity (BMI >30 kg/m²); Comorbidities (see appendix 1); time since HIV diagnosis (years); current ART; CDC disease stage; CD4 cell nadir; last CD4 cell count/HIV-RNA before COVID-19 diagnosis (including CD4% and CD4/CD8 ratio) at baseline. For continuous variables, the decision to treat the variable as a continuous or categorical variable (as tertile) will be based on the lowest Akaike information criterion value for the corresponding univariable conditional logistic regression analysis. Variables achieving P < 0.20 in the univariable analysis will be retained for the multivariable analysis.

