7.5 Procedure(s) to account for missing or spurious data

Multiple imputation using Chained Equations approach (MICE) will be used to fill in missing data. Ten imputations (M=10) will be chosen to obtain valid inference and reduce sampling variability resulting from the imputation process. Variables with a missing rate above 15% will be excluded and the outcomes will be included in the imputation model. All 10 datasets will be analyzed and combined using Rubin rules.

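### CD4 and HIV-RNA are dated before COVID-19 diagnosis in cases but have no reference date in HIV-only controls, so calendar time can be mixed with case status when PLWHIV with and without COVID-19 are compared

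*Combined protocol and SAP*

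**What the plan says.** - **Timing of the covariates (6.2).** For PLWHIV the plan collects "Last CD4 cell count (including CD4% and CD4/CD8 ratio) and HIV-RNA before COVID-19 diagnosis, or most recent for HIV-only controls". One list entry holds two rules, split by case status. The list asks for no date of the CD4 or HIV-RNA measurement.
- **Calendar limit on cases (5.1).** A case needs a "positive result on PCR testing of a nasopharyngeal or respiratory sample, before 1st April 2021". HIV-only controls must have "No evidence of SARS-CoV-2 infection" and carry no date limit.
- **Matching (4.1).** For HIV-only controls, "a 1:2 matching for similar risk of acquiring COVID-19 will be performed according to the following criteria": age, sex and, where available, ethnicity. The criterion "Month of COVID-19 diagnosis (+/- 2 months" appears only for the HIV-seronegative controls.
- **Analysis (7.3.2).** "The second primary outcome analysis will be performed within the group of PLWHIV (PLWHIV with COVID-19 versus PLWHIV without COVID-19". The model is conditional logistic regression. The candidate factors include "last CD4 cell count/HIV-RNA before COVID-19 diagnosis (including CD4% and CD4/CD8 ratio) at baseline". Calendar time is not among them. The same paragraph gives the aim as factors associated with severe COVID-19.
- **Infection-factor analysis (7.1, 7.3).** Section 7.1 sizes a search for factors associated with SARS-CoV-2 infection in PLWHIV, and section 7.3 plans conditional logistic regression for factors associated with COVID-19 in that group.

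**The concern.** In a matched case-control comparison, a time-varying covariate should be read at the same reference point in the case and in its controls. Here the case value stops at a diagnosis before April 2021, while the control value can be as late as the day of chart abstraction. If CD4 rises or HIV-RNA falls over calendar time in people under care, later control values would look better than case values even if neither marker has anything to do with COVID-19. The difference lies within each matched set, so conditioning on the set does not remove it.

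Current CD4 count is one of the factors the study names in its hypothesis (section 3) and in primary objective 2 (section 3.1). An artefact in that variable would therefore be read as an answer to a question the study was set up to ask. Without recorded measurement dates, it might not be possible to detect or adjust for it afterwards.

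**Working it through.** The plan gives no figure on this point to reproduce. The check is a comparison of the text, followed by an illustration on assumed inputs.

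**1. Does any section align the two timing rules?**
- Eligibility (5.1): dates the cases, not the HIV-only controls.
- Matching (4.1): no calendar criterion for HIV-only controls.
- Covariates (7.3.2): no calendar variable. The wording refers only to a COVID-19 diagnosis and omits the section 6.2 rule for controls.
- Collection (6.2): the case's positive PCR date is collected; CD4 and HIV-RNA measurement dates are not listed.

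None does.

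**2. How long could the gap be?** The documents give no abstraction dates. As markers only, the days from 1 April 2021 to the version dates in Appendix 2 are:
- 28 June 2021: 88 days
- 10 November 2021: 223 days
- 29 August 2022: 515 days

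These equal the gap between measurements only if the lag from sample to reference date is similar in both groups. Cases diagnosed earlier than the limit would have longer gaps.

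**3. What could such a gap do?** Take CD4 as a single continuous covariate with no true effect.
- From the plan: 500 cases and 1,000 HIV-only controls (synopsis; this agrees with 1:2 matching, although section 7.1 also prints 1500 controls within a total of 1500 PLWHIV).
- Assumed: SD 250 or 300 cells; drift 0, 5, 10 or 20 cells/year.

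Formulas:
- shift = drift × gap / 365.25
- SE = SD × √(1/500 + 1/1000), which is 13.69 for SD 250 and 16.43 for SD 300
- z = shift / SE
- false-positive rate = Φ(z − 1.96) + Φ(−z − 1.96)

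Example (10 cells/year, 515 days, SD 300): shift = 10 × 515 / 365.25 = 14.10; z = 14.10 / 16.43 = 0.858; rate = Φ(−1.102) + Φ(−2.818) = 13.8%.

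| Drift (cells/year) | SD | 88 days | 223 days | 515 days |
|---|---|---|---|---|
| 0 | either | 5.00% | 5.00% | 5.00% |
| 5 | 300 | 5.06% | 5.40% | 7.13% |
| 5 | 250 | 5.09% | 5.57% | 8.09% |
| 10 | 300 | 5.25% | 6.60% | 13.77% |
| 10 | 250 | 5.36% | 7.31% | 17.75% |
| 20 | 300 | 5.99% | 11.53% | 40.38% |
| 20 | 250 | 6.43% | 14.49% | 53.96% |

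The rate reaches 10% at z = 0.652, a shift of 8.9 cells (SD 250) to 10.7 cells (SD 300). That takes 1.79-2.14 years at 5 cells/year, or 0.45-0.54 years at 20.

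**4. Does the matched model behave the same way?** Univariable 1:2 conditional logistic regression was simulated with 500 sets, 3,000 runs and the covariate independent within sets. The Monte Carlo standard error near 5% is √(0.05 × 0.95 / 3000) = 0.4 points.

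| Drift / SD | 88 days | 223 days |
|---|---|---|
| 0 | 4.8% | 4.6% |
| 5 / 300 | 4.9% | 5.5% |
| 10 / 300 | 5.6% | 6.7% |
| 20 / 275 | 6.5% | 12.1% |

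This agrees with the formula. CD4%, CD4/CD8 ratio and HIV-RNA were not sized.

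**The case against.** **The control value is not undefined.** From section 7.3.2 alone a reader might infer that the covariate does not exist for someone without a diagnosis. Section 6.2 defines it as the latest value available. What is missing is a reference date, and section 7.3.2 fails to carry the control rule over. This objection stands.

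**The primary objective may not be touched.** Primary objective 2 and the second hypothesis in section 7.3 concern severe COVID-19 within PLWHIV, and section 7.3.2 uses the same word for its aim. If the sponsor resolves that paragraph towards severity among cases, all subjects follow one timing rule and the problem disappears there. It would then remain only in the infection-factor analysis of 7.1 and 7.3. This also stands, and it limits the point.

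**The harm is conditional.** A reader might infer from the upper end of the table that a bias has been shown. It has not: drift, SD and gaps are all assumed, and the spread from 5% to 54% mainly reflects those choices. The illustration also departs from the plan, which screens at a univariable P < 0.20, chooses continuous or tertile coding by AIC, and then fits a multivariable model. The rates do not carry over to that procedure.

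**Controls have no diagnosis date, so the latest value is a natural choice.** This does not stand. Each control belongs to a set with a case whose positive PCR date is collected.

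**The same criticism could extend to current ART, comorbidities and the undated infection-free criterion.** A reader might go that far, but section 6.2 sets different rules by case status only for CD4 and HIV-RNA. For the other items no asymmetry is written down.

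**Conclusion.** The point holds as a design weakness that should be corrected, with medium confidence. The plan states two timing rules for the same covariates, and nothing in eligibility, matching or the covariate list brings them together. Calendar time can therefore be mixed with case status in the comparison of PLWHIV with and without COVID-19.

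Neither size nor direction follows from the documents. The effect is nil with no time trend, small at 5 cells/year over the gaps considered, and large only if a drift near 20 cells/year meets a gap of more than a year. Its bearing on primary objective 2 depends on how the severity wording in section 7.3.2 is settled.

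**What to change.** **Change, in sections 6.2 and 7.3.2.**
- Give each HIV-only control an index date equal to the matched case's positive PCR date.
- Take the last CD4 (with CD4% and CD4/CD8 ratio) and HIV-RNA before that date, under the same rule as in cases.
- Record the measurement date in both groups.
- Compute time since HIV diagnosis at the index date; the date of HIV diagnosis is already collected.
- Use the same wording for the covariate in both sections.

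**Cost.** A short amendment; a dated chart look-up for up to 1,000 controls; measurement dates for the 500 cases if the eCRF does not already hold them. Sample size is unchanged.

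**Missing data.** Requiring a value before the index date may leave some controls without one, and under section 7.5 "Variables with a missing rate above 15% will be excluded". The denominator is not stated. Over 1,500 PLWHIV the limit is 0.15 × 1500 = 225 missing values. That is 225 / 1000 = 22.5% of controls if cases are complete, or (225 − 50) / 1000 = 17.5% if 10% of cases (50) are missing. Check this before fixing any look-back window.

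**Fallback.** If the limit would be exceeded, set one common cut-off for control values, for example before 1 April 2021, and add a sensitivity analysis using the measurement dates. This bounds the gap but does not close it for cases diagnosed well before the cut-off.

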7 STATISTICS AND DATA ANALYSIS

7.1 Sample size calculation

The US Veterans Ageing Cohort Study (VACS) reported at AIDS 2020 [20] that the estimated proportion of non-HIV-infected individuals hospitalized with COVID-19 was 35%, 15% in ICU, 8% with invasive mechanical ventilation and 11% died. We anticipate a 1.1 to 2-fold increase in hazard rate in PLWHIV & COVID-19 (cases) relative to HIV-negative & COVID-19 (controls). With 500 cases and 1500 controls, a two-sided log-rank test at an alpha level of 0.05 will achieve at least 80% power to detect a 1.3-fold increase in the hazard rate of hospitalization, 1.4 for ICU, 1.6 for invasive mechanical ventilation and 1.5 for death (refer to Table 1 below). The power calculation was made using the statistical software package nQuery Advanced, with the two samples Log-Rank test module (Version 8.6.1.0).

Table 1

¹ Most recent available after positive SARS-CoV-2 PCR test, up to 10 days after positive test

		Cases (PLWHIV & COVID-19, N=500); Controls (HIV-negative & COVID-19, N=up to 1500) Alpha=5% (two-sided)										
Severity outcome	Outcome (%)	Power (%)										
Hazard Risk		1.1	1.2	1.3	1.4	1.5	1.6	1.7	1.8	1.9	2.0	
Hospitalization	35	20	60	90	99	>99	>99	>99	>99	>99	>99	
ICU	15	11	31	58	81	94	99	>99	>99	>99	>99	
Invasive mechanical ventilation	8	8	19	35	54	73	86	94	98	99	>99	
Death	11	9	24	46	68	85	95	98	>99	>99	>99	

For the search for factors associated with SARS-CoV-2 infection in PLWHIV, the recommended rule of thumb for sample size estimation for multivariable logistic regression models was $n = 100 + 50i$ where i refers to number of independent variables in the final model [34]. With 1500 PLWHIV (500 with COVID-19 and 1500 controls without COVID-19), we would be able to study 28 parameters with sufficient power to produce statistics that are nearly representative of the true values in the targeted population. However, sample size less than 1500 may be sufficient for associations that yield medium to large effect size.

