3.3 Primary endpoint/outcome

1. The primary endpoint is a composite of: Critical care admission (high dependency unit or intensive care unit), mortality in hospital or palliative discharge when discharged from hospital, or mortality at 6 weeks after diagnosis of COVID-19 or at discharge from hospital (where applicable)

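### Unequal 1:1 and 1:3 matching unbalances inpatient status between the HIV groups, 7.3.2 does not include setting, and the 80% power in 7.1 assumes a control count that this matching does not give

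*Combined protocol and SAP*

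**What the plan says.** Section 7.1 rests the power on an unstratified two-sample log-rank test: "With 500 cases and 1500 controls, a two-sided log-rank test at an alpha level of 0.05 will achieve at least 80% power". The hazard ratios are 1.3 for hospitalisation, 1.4 for ICU, 1.6 for invasive ventilation and 1.5 for death. The Table 1 header describes 1,500 as an upper limit, but the table gives no power for fewer controls.

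Section 4.1 sets the ratio by setting at diagnosis: "COVID-19 diagnosis inpatient, 1:1 matching" for one group and 1:3 for outpatients. Section 5.1 repeats it: "Each case should be matched to a control (1:1 or 1:3 respectively for COVID-19 controls and 1:2 for PLWHIV controls"). Section 6.2 collects the variable ("COVID-19 diagnosis inpatient or outpatient") and asks for unbiased matching on it.

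Section 7.3.2 introduces the covariates of the first primary Cox model with "The adjusted variables will be the following (potential confounders): Age" and continues with sex, obesity and comorbidities. It names no setting term, setting stratum or matched-set stratum. Matching is accounted for only in the conditional logistic model within PLWHIV. Section 7.3.3 reuses the same covariates for the secondary Cox analyses.

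The endpoint in 3.3 is a composite ("The primary endpoint is a composite of: Critical care admission (high dependency unit or intensive care unit", together with death or palliative discharge). Table 1 has no row for it.

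**The concern.** A constant matching ratio would keep inpatient status balanced between HIV-positive and HIV-negative patients. Two different ratios undo that balance when the strata are pooled: outpatients are over-represented among controls three to one relative to inpatients. If inpatients at diagnosis have a higher risk of critical care or death, a model without setting attributes part of that difference to HIV. At stake is the first primary objective, whether HIV infection worsens COVID-19 outcomes, because the sampling ratio alone could produce a positive answer.

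The power statement has a related fault. It describes a sample that the matching gives only in an extreme case, and a pooled test that would be biased under this design.

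**Working it through.** **Inputs.** From 7.1: 500 cases; control risks 35% (hospitalisation), 15% (ICU), 8% (ventilation), 11% (death); the hazard ratios above; two-sided alpha 0.05. From 4.1: ratios 1:1 and 1:3. From 6.1: "1,187 PLWHIV with COVID-19 were reported in care across Europe, with 436 hospitalisations and 78 deaths". Two quantities are not in the documents and are assumed over ranges:
- f, the inpatient share of cases at diagnosis. Proxies are 35% (7.1) and 436/1,187 = 36.7% (6.1), both of them hospitalised at any time; 15–20% is a lower alternative.
- s, the share of severe events arising in inpatients, taken as 60–100%.

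**1. Reproducing Table 1.** Freedman's formula is power = Φ(√(d·r)·(HR−1)/(1+r·HR) − 1.96), with r = cases/controls and d = 500·[1−(1−p)^HR] + controls·p. For ICU, d = 101.7 + 225 = 326.7 and r = 1/3, so power = Φ(2.846 − 1.96) = 81.2%. The four outcomes give 90.8/81.2/86.2/85.4% against the stated 90/81/86/85%. Table 1 is correct for its own inputs.

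**2. Control count.** Controls = 500·[f + 3(1−f)] = 1,500 − 1,000f. Power by the same formula:

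| f | Controls | Hosp. | ICU | Vent. | Death |
|---|---|---|---|---|---|
| 0 | 1,500 | 90.8 | 81.2 | 86.2 | 85.4 |
| 15% | 1,350 | 89.8 | 79.8 | 84.9 | 84.1 |
| 20% | 1,300 | 89.4 | 79.3 | 84.4 | 83.6 |
| 35% | 1,150 | 88.1 | 77.5 | 82.6 | 81.8 |
| 36.7% | 1,133 | 87.9 | 77.3 | 82.4 | 81.6 |

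ICU falls below 80% once f passes about 14%. The other three stay above it over this range.

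**3. Imbalance and bias.** The inpatient share of controls is f/(3−2f), which at f = 36.7% is 0.367/2.265 = 16.2%. With no HIV effect and case risk p, control risk is p(3−2s)/(3−2f), so the crude risk ratio is (3−2f)/(3−2s):
- f = 36.7%: 2.265/1.8 = 1.26 (s = 60%), 2.265/1.5 = 1.51 (s = 75%), 2.265/1 = 2.27 (s = 100%).
- f = 20%: 2.6/1.8 = 1.44 (s = 60%), 2.6/1.5 = 1.73 (s = 75%).

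Simulated false-positive rates at f = 36.7% (exponential times, administrative censoring, 2,000 replicates), for s = 60/75/100%, are ICU 40/83/100%, ventilation 24/54/98% and death 31/69/100%. They are about 5% when s = f, and 4–7% when the test is stratified by setting.

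**4. Power after stratifying.** Schoenfeld's formula is used with information summed over settings, Σ E·w·(1−w), where E is events and w the case share in the stratum (1/2 for inpatients, 1/4 for outpatients). The 7.1 risks are taken to hold for HIV-negative patients with the cases' inpatient mix. Example, ICU with f = 36.7% and s = 75%: stratum risks 0.306 and 0.059, events about 130 and 82, information 32.5 + 15.4 = 47.9, power = Φ(√47.9 × ln 1.4 − 1.96) = 64%. For f = 35–36.7% and s = 60–100%:

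| | Pooled, 1,500 (Schoenfeld) | Stratified (Schoenfeld) | Stratified (simulated) | HR for 80%: pooled, then stratified |
|---|---|---|---|---|
| ICU | 75 | 59–67 | 59–70 | 1.43, then 1.48–1.53 |
| Ventilation | 79 | 65–72 | 64–75 | 1.61, then 1.67–1.73 |
| Death | 79 | 64–71 | 63–74 | 1.51, then 1.56–1.62 |

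Power simulations for these rows used 3,000 replicates. Hospitalisation is left out because a patient diagnosed as an inpatient is already in hospital.

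**5. Composite.** With an assumed control risk of 18–20% and HR 1.4, pooled Freedman power with 1,133 controls is 84–88%; stratified simulated power is 66–81%.

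**6. Event-rate sensitivity.** The dashboard death rate in PLWHIV is 78/1,187 = 6.6%. At HR 1.5 the control risk is 1−(1−0.0657)^(1/1.5) = 4.4%, and d = 32.9 + 66.4 = 99.3 with 1,500 controls. Freedman power is 48% (45% with 1,133 controls); Schoenfeld gives 42% and 40%.

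**7. Second comparison.** Section 7.1 describes 1,500 PLWHIV as "500 with COVID-19 and 1500 controls without COVID-19", which sums to 2,000. The synopsis gives 1,000 such controls; 500 + 1,000 = 1,500, and 100 + 50 × 28 = 1,500.

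**The case against.** Table 1 is not an arithmetic error, and the synopsis, 4.1 and the table header all present the control number as a maximum. The count effect is small. Both points stand, so the weight of the concern lies on the omission of setting in 7.3.2.

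The size of the bias depends on f and s, neither of which the documents give, and hospitalised at any time is not the same as diagnosed as an inpatient. That also stands: at s = 50% the ratio at f = 36.7% is only 2.265/2 = 1.13. The direction does not depend on those values. For any f between 0 and 100% the bias disappears only if inpatients at diagnosis carry no higher risk than outpatients, which is implausible for critical care and death. Adjusting for age, sex, obesity and comorbidities may absorb some of the difference, but cannot be relied on to remove an imbalance created by the ratios, and the pooled Kaplan–Meier estimates are not adjusted at all.

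ICU admission, ventilation and death are Table 1 outcomes rather than endpoints listed on their own, so low power for them does not show that the composite is underpowered. That is accepted. Part of the gap between the stratified detectable hazard ratios and the stated 1.4, 1.6 and 1.5 is formula rather than design: pooled Schoenfeld with 1,500 controls already needs 1.43, 1.61 and 1.51. The dashboard death rate has no stated follow-up window and belongs only in a sensitivity row.

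Stratification is not the only remedy; weighting controls by the inverse of their matching ratio would also restore balance.

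**Conclusion.** The concern holds. From the documents alone, 1,500 controls is a ceiling reached only with no inpatient cases, any mixture of settings leaves the pooled groups unequal in inpatient share, and the first primary model ignores setting.

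The main consequence is bias towards finding harm from HIV. Under the 36.7% proxy, and with 60–75% of severe events in inpatients, the spurious ratio of 1.26–1.51 is of the same order as the effects the study is powered to detect. A lower inpatient share does not cure this.

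The power consequence is secondary: a few points from the lower count, and more once the analysis is stratified, which leaves ICU, ventilation and death below 80% at the stated hazard ratios in the scenarios examined. Low power for the composite is possible but not shown. All sizes rest on the assumed f and s; the contradiction itself does not.

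**What to change.** 1. In 7.3.2, stratify the Cox and log-rank analyses of the first comparison by inpatient or outpatient status at diagnosis, and present Kaplan–Meier curves by setting. Carry this into the Cox analyses in 7.3.3, which reuse the same covariates.
2. Restate 7.1 and Table 1 for the stratified analysis: control numbers and power over a stated range of inpatient shares (for example 15–37%) and event shares (for example 60–100%), the hazard ratio detectable with 80% power, and a row for the composite primary endpoint. Label the present Table 1 as the ceiling that applies only if every case is an outpatient.
3. Show the dashboard death rate as a separate sensitivity row.
4. Correct the number of PLWHIV controls without COVID-19 in 7.1 to 1,000.

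The cost is one stratification term on a variable already collected, and power figures that are less favourable but match the design. These changes need no new data and no extra patients.

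### The power stated in section 7.1 is for 1,500 controls at whole-cohort event rates, which the 1:1 inpatient / 1:3 outpatient matching does not produce

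*Combined protocol and SAP*

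**What the plan says.** Section 7.1 takes its control event proportions from a cohort of HIV-negative people with COVID-19: "hospitalized with COVID-19 was 35%, 15% in ICU, 8% with invasive mechanical ventilation and 11% died". It then claims: "With 500 cases and 1500 controls, a two-sided log-rank test at an alpha level of 0.05 will achieve at least 80% power", for a "1.3-fold increase in the hazard rate of hospitalization, 1.4 for ICU, 1.6 for invasive mechanical ventilation and 1.5 for death". The software is given as "nQuery Advanced, with the two samples Log-Rank test module (Version 8.6.1.0"), a two-group calculation with no stratum term. The text uses 1,500 as a fixed number, while the Table 1 header reads "Controls (HIV-negative & COVID-19, N=up to 1500").

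Section 4.1 sets the matching ratio by setting at diagnosis: "COVID-19 diagnosis inpatient, 1:1 matching" or "COVID-19 diagnosis outpatient (ambulatory), 1:3 matching". Appendix 2 lists the rise to 1,500 controls and the 1:3 wording under the same amendment. No section gives the expected share of cases diagnosed as inpatients, or event rates by setting of diagnosis. The Cox model in section 7.3.2 adjusts for age, sex, obesity and comorbidities. It lists neither setting at diagnosis nor the matched set.

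**The concern.** Log-rank power depends on the number of events. Table 1 implies 225 ICU events, 120 ventilation events and 165 deaths among controls (1,500 x 15%, 8% and 11%). The matching rule works against those counts in two ways. It yields fewer than 1,500 controls as soon as any case is inpatient-diagnosed. It also draws every control beyond the first from outpatient diagnoses, who are plausibly at lower risk of critical care and death, although some will be admitted later.

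If the stated power is too high, a null finding on severe outcomes could be read as the result of an adequately powered study. A second consequence concerns validity. A control group tilted towards outpatients, compared with cases without regard to setting, makes HIV look more harmful than it is.

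**Working it through.** **Inputs.** From 7.1: 500 cases, 1,500 controls, two-sided alpha 0.05, control rates p = 0.15, 0.08 and 0.11, and hazard ratios 1.4, 1.6 and 1.5. From 4.1: ratios 1:1 and 1:3. Proxy for the inpatient share f: 35% hospitalised in the cohort cited in 7.1, and 436/1,187 = 36.7% in section 6.1. Both are ever hospitalised, not inpatient at diagnosis. Assumed: the share s of control-population events that arise in inpatient diagnoses, varied from f (setting carries no prognostic information) to 1.

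**Step 1: reproduce Table 1.** Freedman's formula with φ = cases/controls, case rate 1 - (1 - p)^HR and D total events:

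power = Φ( √(Dφ) (HR - 1)/(1 + φHR) - 1.96 )

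For ICU, D = 500 x 0.2035 + 1,500 x 0.15 = 326.7 and φ = 1/3, giving 81.2%. Ventilation gives 86.2% and death 85.4%. The printed values are 81, 86 and 85, so Table 1 is right for its own inputs and uses the full 1,500.

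**Step 2: number of controls.** 500f + 3 x 500(1 - f) = 500(3 - 2f). This is 1,150 at f = 0.35 and about 1,133 at f = 0.367. It is 1,500 only at f = 0. The lower count alone, still unstratified and at cohort rates, takes ICU at 1,150 controls to 77.5% (D = 274.2, φ = 0.435).

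**Step 3: control events.** If cases have the same mix as the reference cohort, control rates are ps/f (inpatient) and p(1 - s)/(1 - f) (outpatient). Control events are then 500ps + 1,500p(1 - s) = 500p(3 - 2s), which is (3 - 2s)/3 of the number Table 1 assumes.

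**Step 4: power stratified by setting.** With π1 = φHR/(1 + φHR) and π0 = φ/(1 + φ) in each stratum:

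power = Φ( Σ D(π1 - π0) / √(Σ D π0(1 - π0)) - 1.96 )

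Worked case, ICU, f = 0.35, s = 0.75:
- Inpatient: 175 v 175, control rate 0.3214, case rate 0.4189, D = 129.6, π1 - π0 = 0.0833.
- Outpatient: 325 v 975, control rate 0.0577, case rate 0.0798, D = 82.2, π1 - π0 = 0.0682.
- Numerator 10.80 + 5.60 = 16.40; variance 32.40 + 15.41 = 47.81; z = 16.40/6.91 = 2.37; power = Φ(0.41) = 66%.

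Results at f = 0.35-0.367:

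| s | Control events, % of assumed | ICU, HR 1.4 | Ventilation, HR 1.6 | Death, HR 1.5 |
|---|---|---|---|---|
| s = f | 76-77 | 75% | 80% | 79-80% |
| 0.50 | 67 | 72% | 77% | 77% |
| 0.75 | 50 | 66% | 71% | 70-71% |
| 1.00 | 33 | 59% | 63% | 63% |
| Printed | 100 | 81% | 86% | 85% |

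In this range ICU is below 80% throughout. Death is at or just below 80% at best. Ventilation holds 80% only up to s of about 0.37.

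**Step 5: sensitivity to the proxy.** At f = 0.20 (1,300 controls) power for ICU / ventilation / death is 78 / 83 / 82% at s = f and 65 / 70 / 70% at s = 0.75.

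**Step 6: relax the cohort-mix assumption.** Hold the setting-specific rates at those implied by f = 0.35 and s = 0.75, and let the inpatient share of cases rise. At 70% inpatient there are 800 controls and power is 81 / 86 / 85%. At 100% there are 500 controls and power is 89 / 92 / 92%.

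**Step 7: effect of ignoring setting.** At a true HR of 1 and f = 0.367, the pooled control ICU rate is 0.15(3 - 2s)/(3 - 2f). That is 0.132 at s = 0.50 and 0.099 at s = 0.75, against 0.15 in cases. The apparent hazard ratio, ln(0.85)/ln(1 - control rate), is about 1.14 and 1.55.

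**The case against.** The strongest reply is that the documents fix neither the case mix nor the risk by setting, so no shortfall is proven. That stands. Step 6 shows that inpatient-weighted cases can restore 80% with far fewer controls, and section 6.2 foresees hospital-diagnosed controls drawn from cohort databases. Control events are independent of the inpatient share of cases only if that share equals the reference population's. Even so, a sample with 70% inpatients has 800 controls, so section 7.1 would still describe a different study.

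Other fair points:
- The table header already calls 1,500 a ceiling. True, but the power is computed at the ceiling, which the matching rule reaches only with no inpatient-diagnosed case.
- Part of the drop comes from stratifying, which the plan does not specify. This is so: at 1,150 controls and no risk difference, ICU is 77.5% unstratified and 75.2% stratified. Step 7 shows why the unstratified comparison is not a sound alternative once setting predicts outcome.
- The primary endpoint is a composite with at least as many events as ICU alone, and section 7.1 gives no power for it. The figures here therefore concern the three Table 1 rows, not the primary endpoint.
- High s combined with low f is implausible: f = 0.20 and s = 1 would put 75% of inpatient-diagnosed controls in ICU, against 15/35 = 43% of those hospitalised on the plan's own figures.

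A reader might infer that about half of the assumed control events will occur. That needs s of about 0.75, which the documents do not supply.

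**Conclusion.** The point holds as a mismatch between the power calculation and the sampling design. Table 1 is arithmetically correct for 500 against 1,500 at cohort rates, but the matching rule in section 4.1 changes both the number of controls and their risk, and section 7.1 accounts for neither.

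If cases keep the cohort mix at a 35-37% inpatient share, with the same hazard ratio in both settings, full matching and a stratified analysis, power is about 59-75% for ICU, 63-80% for ventilation and 63-80% for death. The range comes from s, which is assumed throughout. The inpatient share rests on a proxy.

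It would go too far to conclude that the study cannot reach 80% power for severe outcomes. The documents support only that the stated power does not describe the design as written, and that it is too high under the case mix their own hospitalisation figures suggest.

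**What to change.** In section 7.1, state the expected share of cases diagnosed as inpatients and the control event rates by setting, with a range where they are uncertain. Recompute the ICU, ventilation and death rows of Table 1 in two strata (1:1 inpatient, 1:3 outpatient), using a log-rank test or Cox model stratified by setting at diagnosis. Replace the sentence claiming at least 80% power with the recomputed power at the quoted hazard ratios, or with the ratios that reach 80%. As a guide, at f = 0.35 and s = 0.6-0.8 the step 4 formula gives about 1.46-1.49 for ICU, 1.64-1.69 for ventilation and 1.54-1.58 for death.

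In section 7.3.2, stratify the Cox model for the HIV comparison by inpatient/outpatient status at diagnosis, so that the unequal ratio does not push the HIV hazard ratio upward.

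The cost is a recalculation and revised wording. Setting at diagnosis is already collected under section 6.2, and no extra patients are needed. The downside is a less favourable stated power.
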